8.1.7. Secondary Safety Endpoints

- (1) Rate of conversion to thoracotomy or secondary intervention. Whether subjects require

conversion to open thoracic surgery or secondary interventional procedures due to new-onset aortic dissection caused by the index procedure.

- (2) Rate of major adverse events occurring within 30 days after surgery. Refers to all-cause mortality, myocardial infarction, ischemic stroke or respiratory failure occurring within 30 days after surgery. More specifically, myocardial infarction refers to a drastic reduction or complete interruption of the coronary blood supply due to coronary artery disease, resulting in severe and prolonged acute ischemia of the corresponding myocardium, leading to necrosis of cardiomyocytes. Ischemic stroke refers to the end result of necrosis of brain tissue caused by narrowing or occlusion of the arteries supplying blood to the brain or insufficient blood supply to the brain. Respiratory failure is defined as a state resulting in significantly prolonged intubation, tracheotomy, deterioration of lung function, or other fatal outcomes.
- (3) Rate of aortic aneurysm-related mortality at 12 months post operation. Refers to mortality caused by a ruptured aortic aneurysm or endovascular interventional treatment.
- (4) Incidence of severe adverse events. Refers to an event that occurs during the clinical trial that results in mortality or serious deterioration in patient health, including a fatal illness or injury, a permanent defect in body structure or body function, or an event that requires medical or surgical intervention to avoid one or more permanent defects in body structure or body function.
- (5) Incidence of device-related adverse events. Device-related adverse events refer to an adverse medical event related to the use of a device that occurs during the course of the clinical trial. However, a distinction should be made with respect to normal postoperative stress response, such as fever and chest and back discomfort, which, in the judgment of the investigator, need not be recorded as an adverse event. Recording device-related adverse events will be applicable for conditions that are deemed by the investigator to be definitely related, possibly related, or of indeterminate relationship, to the test device.

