(7) During advancement and positioning of the aortic extension stent graft system, the positional relationship between its proximal radiopaque markers and the distal radiopaque markers of the previously deployed integrated aortic arch segment stent graft shall be considered.

(8) After accurate positioning of the integrated ascending aortic stent graft, integrated aortic arch segment stent graft, aortic extension stent graft, and branched stent grafts, the handle position shall remain stationary until full deployment of all stent grafts; otherwise, inaccurate stent

positioning may occur.

(9) When the proximal or distal end of the integrated ascending aortic stent graft is adjacent to critical arterial branches (e.g., coronary arteries, innominate artery, etc.), angiography or other imaging modalities may be used to assist positioning and prevent coverage or occlusion of vital branch vessels by the graft fabric.

(10) Once the integrated aortic arch segment stent graft system contacts the integrated ascending aortic stent graft during advancement, no further upward pushing of the delivery system shall be attempted for positional adjustment; otherwise, severe consequences such as migration of the integrated ascending aortic stent graft, vascular injury, or stent deformation may occur.

(11) During selective catheterization of the two integrated branches of the integrated ascending aortic stent graft, full confirmation that the guidewire passes entirely through the integrated branch lumens is mandatory.

(12) This device consists of the integrated ascending aortic stent graft system, integrated aortic arch segment stent graft system, aortic extension stent graft system, and branched stent graft system. Each component is preloaded in its dedicated delivery system and individually packaged.

(13) The Modular Integrated Triple-Branched Aortic Arch Stent Graft System is sterilized with ethylene oxide prior to factory release.

(14) This device is intended for single-use only. The manufacturer assumes no liability for cross-infection or adverse outcomes resulting from unauthorized reuse of any stent graft, delivery system, or component of this device. Do not use the product if the sealed packaging is damaged prior to opening.

8. Overall Design

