Considering the high clinical risk associated with ascending aortic and aortic arch diseases, and the anatomical proximity of the implant site to the aortic valve, the Guidelines for the Design of Medical Device Clinical Trials emphasize that primary endpoints should directly reflect clinical benefits and safety of the device. Accordingly, the primary endpoint of this trial is defined as the 12-month composite incidence of all-cause death or major stroke. In reference to the Guidelines for Clinical Trials of Aortic Stent Graft Systems, efficacy endpoints include the incidence of Type I or Type III endoleak, aortic stent graft migration rate, postoperative branch vessel patency rate, and conversion rate to open thoracic surgery or secondary interventional procedures. Safety endpoints comprise all-cause mortality, the incidence of serious adverse events, and the incidence of device-related adverse events. The objective performance criterion is established based on comprehensive, scientifically robust evidence from comparable marketed devices, while taking technological progress into account to ensure prospective rationality.

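### The reintervention rate and the 30-day infarction component are defined more narrowly than their names, so both descriptive rates can understate what they claim to report

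*Protocol*

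**What the plan says.** **Reintervention.** Section 8.1.7 (1), repeated in the Trial Protocol Summary, has a general title covering conversion to thoracotomy or secondary intervention. The definition beneath it is narrower. It asks whether subjects require "conversion to open thoracic surgery or secondary interventional procedures due to new-onset aortic dissection caused by the index procedure". Section 8.1.2 lists the endpoint simply as "conversion rate to open thoracic surgery or secondary interventional procedures". Sections 4.2 and 9.4.2 (item 4) also name it without a cause. Sections 4.2 and 8.1.2 place it among the effectiveness endpoints, whereas section 8.1.7 places it under safety.

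**30-day major adverse events.** Section 8.1.7 (2) defines the composite as "all-cause mortality, myocardial infarction, ischemic stroke or respiratory failure occurring within 30 days after surgery". It then specifies that "myocardial infarction refers to a drastic reduction or complete interruption of the coronary blood supply due to coronary artery disease". The Summary carries the same text.

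**Device risks the protocol names.** Section 14.4.3 lists malposition, migration, stent breakage, endoleak and rupture of the coating as device complications. Section 8.1.6 follows endoleak, displacement and branch patency as secondary efficacy endpoints. Section 7.3, caution (9), deals with the ascending graft lying "adjacent to critical arterial branches (e.g., coronary arteries, innominate artery, etc" and warns that the fabric may cover or occlude such vessels.

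**Analysis.** Section 9.4.2 reports the secondary safety endpoints as frequencies and percentages only, mainly in the Safety Set.

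**The concern.** A reader who sees a reintervention rate for a modular arch graft will take it as the share of subjects who needed another procedure. Under the definition it is the share who needed one because the index procedure caused a new dissection. The device is indicated for aneurysm, pseudoaneurysm and ulcer (section 7.1), and most complications listed in section 14.4.3 would lead to a further procedure for some other reason.

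The infarction wording has the same kind of gap. The mechanism that caution (9) points to, graft fabric over a coronary artery, is not coronary artery disease. Read literally, such an infarction is not a 30-day major adverse event unless the subject dies or has another component.

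Both rates are among the safety results the sponsor will summarise after the 12-month follow-up and submit to the regulator (sections 4.2 and 8.1.4.6). Two analysts, one working from section 8.1.7 and one from the unrestricted name in section 9.4.2, could report different numbers under the same label.

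**Working it through.** The point is about definitions, so the main check sets the sections against each other. Arithmetic gives only the scale.

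**1. Which procedures count under 8.1.7 (1)?**

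| Reason for the procedure | Named in the protocol | Secondary intervention counted? |
|---|---|---|
| New dissection caused by the index procedure | 8.1.7 (1) | Yes |
| Endoleak | 8.1.6 (3), 14.4.3 | No |
| Migration | 8.1.6 (4), 14.4.3 | No |
| Branch occlusion | 8.1.6 (5) | No |
| Stent breakage, malposition | 14.4.3 | No |

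The grammar leaves one ambiguity. The dissection clause may qualify both conversion and secondary procedures, or only secondary procedures. On the second reading every conversion to open surgery counts, but the table stands for secondary interventions. Section 8.1.6 counts the leak, the displacement or the loss of patency, not whether it required another procedure. No other endpoint supplies a reintervention rate.

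**2. Which infarctions are missed under 8.1.7 (2)?** Three conditions must all hold: the infarction is not due to coronary artery disease, the subject survives 30 days, and the subject has neither ischemic stroke nor respiratory failure in that window. If any one fails, the subject is already counted.

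**3. Denominator.** Section 8.1.4.8 gives 72 evaluable subjects and 20% dropout: 72 / (1 − 0.20) = 90, which reproduces the stated total. One subject is 1/90 = 1.1 percentage points.

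**4. Scale of the reintervention gap (assumed inputs).** The protocol gives no event rates. Let r be the all-cause rate and s the share due to new dissection. Reported rate = r × s. Uncounted subjects = 90 × r × (1 − s).

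| r | s | Reported | Uncounted of 90 |
|---|---|---|---|
| 5% | 10% | 0.5% | 4.0 |
| 5% | 50% | 2.5% | 2.2 |
| 10% | 25% | 2.5% | 6.8 |
| 15% | 10% | 1.5% | 12.2 |
| 15% | 50% | 7.5% | 6.8 |

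Over this range the endpoint shows 0.5% to 7.5% where the all-cause rate is 5% to 15%, and about 2 to 12 subjects go uncounted. This takes the dissection limit as applying to conversions too; on the other reading of the clause the gap is smaller.

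**5. Would an excluded event occur at all?** If a proportion q of subjects has one, the chance of at least one among 90 is 1 − (1 − q)^90. This is 0.60 for q = 1%, 0.84 for 2% and 0.99 for 5%. These q values are also assumptions.

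**The case against.** **Captured elsewhere.** The underlying events are not lost. Adverse events are recorded from Visit 2 (section 8.2.1 notes). Events needing intervention to avoid permanent harm fall under secondary safety endpoint (4), device-related events under (5), and the imaging failures have their own endpoints. This stands, and it limits the consequence. It does not supply the missing rate, because those endpoints pool many kinds of event or count the finding rather than the repeat procedure.

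**Descriptive endpoints.** Neither rate is tested, and trial success depends on the primary endpoint against the performance criterion (section 9.4.2). This also stands.

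**A short name with a narrower definition is only a labelling mismatch.** In part. The other sections only name the endpoint in lists. But here the definition removes most of the reasons the name would lead a reader to expect.

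**Stronger readings that the documents do not support.**
- A reader might infer that the rates will be falsely low, or close to zero. That depends on an excluded event occurring, and the protocol gives no rate to show how often.
- A reader might infer that every infarction from graft coverage or embolism drops out. It does not: all-cause death is in the same composite, so fatal cases count, as does any subject with another component.
- A reader might add haemorrhagic stroke to the exclusions. The component is openly labelled and defined as ischemic, nothing in the protocol calls haemorrhagic stroke device-caused, and major stroke in the primary endpoint is not limited by type.

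**Conclusion.** The point holds for two definitions. Section 8.1.7 (1) counts secondary interventions, and on one reading conversions too, only when due to new dissection caused by the index procedure. That conflicts with its title and with sections 4.2, 8.1.2 and 9.4.2. Section 8.1.7 (2) omits a non-fatal infarction not due to coronary artery disease when the subject has no other component, although caution (9) warns of graft coverage where the coronary arteries are adjacent.

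Both rates can be equal to or below the rate their names describe, never above it. The ranges in the working rest on assumed event rates and illustrate scale only. The primary analysis is not touched. The wording should be corrected, but it does not threaten the trial's main conclusion.

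**What to change.** Make these changes in section 8.1.7 and the Trial Protocol Summary, and reconcile them with sections 4.2, 8.1.2 and 9.4.2:

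1. Endpoint (1): count any conversion to open surgery and any secondary intervention on the treated aorta, its branches or the device, whatever the cause, through 12 months. Tabulate the cause: dissection, endoleak, migration, branch occlusion, rupture, other. The dissection-only figure then remains available as one row. State once whether the endpoint is efficacy or safety.
2. Endpoint (2): delete the phrase that ties infarction to coronary artery disease, so that acute myocardial infarction of any mechanism within 30 days counts.

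The cost is small: an amendment to the protocol wording, matching text in the statistical analysis plan, and a cause field in the eCRF if there is none. Adverse events are already recorded from Visit 2, so no visit or examination is added. The reported rates may come out slightly less favourable.

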	
the index procedure.
 
 2. Rate of major adverse events occurring within 30 days after surgery. Refers to all-cause mortality, myocardial infarction, ischemic stroke or respiratory failure occurring within 30 days after surgery. More specifically, myocardial infarction refers to a drastic reduction or complete interruption of the coronary blood supply due to coronary artery disease, resulting in severe and prolonged acute ischemia of the corresponding myocardium, leading to necrosis of cardiomyocytes. Ischemic stroke refers to the end result of necrosis of brain tissue caused by narrowing or occlusion of the arteries supplying blood to the brain or insufficient blood supply to the brain. Respiratory failure is defined as a state resulting in significantly prolonged intubation, tracheotomy, deterioration of lung function, or other fatal outcomes. 3. Rate of aortic aneurysm-related mortality at 12 months post operation. Refers to mortality caused by a ruptured aortic aneurysm or endovascular interventional treatment. 4. Incidence of severe adverse events. Refers to an event that occurs during the clinical trial that results in mortality or serious deterioration in patient health, including a fatal illness or injury, a permanent defect in body structure or body function, or an event that requires medical or surgical intervention to avoid one or more permanent defects in body structure or body function. 5. Incidence of device-related adverse events. Device-related adverse events refer to an adverse medical event related to the use of a device that occurs during the course of the clinical trial. However, a distinction should be made with respect to normal postoperative stress response, such as fever and chest and back discomfort, which, in the judgment of the investigator, need not be recorded as an adverse event. Recording of device-related adverse events will be applicable for conditions that are deemed by the investigator to be definitely related, possibly related, or of indeterminate relationship, to the test device.
Trial Visitation Plan	
 ➤ Visit 1: Screening period (Day -15 to 0) ➤ Visit 2: Day of Surgery (Intraoperatively, after completion of stent-graft deployment) (Day 0)

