4) Secondary Endpoints

Technical success immediately post-procedure, aortic aneurysm progression control rate, incidence of Type I or Type III endoleak, incidence of aortic stent graft migration, postoperative patency rate of branch vessels, incidence of conversion to open thoracic surgery or secondary interventional procedure, major adverse event rate within 30 days post-operation, aortic aneurysm-related mortality at 12 months post-operation, incidence of serious adverse events, and incidence of device-related adverse events.

Statistical description shall be performed for secondary efficacy indicators, with frequencies and percentages calculated. FAS (Full Analysis Set) and PPS (Per Protocol Set) analyses shall also be conducted.

Statistical description shall be performed for secondary safety indicators, with frequencies and percentages calculated. The SS (Safety Set) analysis shall be adopted as the primary approach.

The Kaplan-Meier method shall be used to estimate the survival rate and its 95% confidence interval, with Kaplan-Meier curves plotted accordingly.

Descriptive statistical analysis shall be performed for the changes of all laboratory parameters before and after the trial. All adverse events occurring during the trial shall be recorded in detail; descriptive statistical analysis of adverse events shall be conducted with a list attached.

In addition to the above statistical methods, detailed and additional exploratory analyses may be required, which shall be confirmed in the Study Report and Statistical Analysis Plan (SAP)..

9.5. Statistical methods for all data, including the handling of missing, unused or erroneous data (including premature discontinuation and withdrawal) and inconsistent data.

A Statistical Analysis Plan (SAP) shall be developed prior to study initiation. After database lock, statistical analysis shall be performed in accordance with the SAP, and a statistical analysis report shall be generated based on the results.

(1) Handling of missing data: Missing data shall be handled according to the analysis set in which they are included. Missing data for the primary endpoint in the Full Analysis Set (FAS) shall be classified by reason as follows:

Missing data clearly due to unsatisfactory efficacy: loss to follow-up or missing primary efficacy data resulting from adverse events, death, etc., related (or possibly related) to the investigational device or aortic dissection.

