14.1.1. Severity Assessment of Adverse Events

Mild: Symptoms are slight and do not interfere with normal daily activities, generally, no treatment is required, and symptoms are resolved spontaneously.

Moderate: Symptoms are sufficient to cause discomfort and interfere with normal daily activities; treatment may be required.

Severe: Symptoms result in significant discomfort; may lead to subject withdrawal from the trial; may result in discontinuation of treatment with the investigational device; specific treatment is required.

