14.2. Severe Adverse Events

A Serious Adverse Event refers to any untoward medical occurrence during a clinical trial of a medical device that results in death or severe deterioration of health status, including fatal disease or injury, permanent impairment of body structure or function, requirement for hospitalization or prolongation of hospitalization, medical intervention required to prevent permanent impairment of body structure or function, fetal distress, fetal death, congenital anomaly or congenital defect.

Planned hospitalization due to a pre-existing disease or surgery specified in the clinical trial protocol that does not cause severe deterioration of health status shall not be regarded as a Serious Adverse Event.

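### The serious adverse event endpoint omits the hospitalisation criterion named in the protocol's own SAE definition, and nothing says which definition governs the count

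*Protocol*

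**What the plan says.** **The endpoint.** Protocol 8.1.7 Secondary Safety Endpoints, item (4), reads: "Incidence of severe adverse events. Refers to an event that occurs during the clinical trial that results in mortality or serious deterioration in patient health". It continues: "including a fatal illness or injury, a permanent defect in body structure or body function, or an event that requires medical or surgical intervention", the intervention being one needed to avoid permanent defects. Item (4) of the safety endpoints in the Trial Protocol Summary has the same title and the same definition. Neither place mentions hospitalisation or refers to another section.

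**The SAE definition.** Section 14.2 is headed Severe Adverse Events, but its text defines the serious event: "A Serious Adverse Event refers to any untoward medical occurrence during a clinical trial of a medical device that results in death or severe deterioration", the deterioration being in health. Its list includes "permanent impairment of body structure or function, requirement for hospitalization or prolongation of hospitalization", followed by medical intervention to prevent permanent impairment and by fetal and congenital outcomes. A second paragraph excludes planned hospitalisation for a pre-existing disease or protocol surgery, provided it causes no severe deterioration.

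**The name used elsewhere.** Section 9.4.2, item 4), lists the endpoint as "incidence of serious adverse events". Sections 4.2 and 8.1.2 also say serious, and 4.2 adds the abbreviation SAEs. Section 14.1.1 uses the other word for an intensity grade: "Severe: Symptoms result in significant discomfort".

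**Analysis.** Under 9.4.2 the secondary safety endpoints are described by frequencies and percentages, primarily in the Safety Set.

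**The concern.** The protocol defines this endpoint itself, and not in the way it defines the SAEs that sites must report. The conflict is therefore in the protocol's own text. It is not a detail left for the analysis plan to supply.

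Unplanned readmission and prolonged stay are routes by which an event becomes serious under 14.2 without death, permanent damage or an intervention to prevent it. An analyst who programs the endpoint from 8.1.7(4) could leave such events out. An analyst who counts the events flagged as SAEs would include them. Both could say that they followed the protocol.

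The trial has a single arm, so the SAE percentage is read as it stands. No control group is counted under the same rule, so a narrower rule would not cancel out in a comparison. A rate based on 8.1.7(4) would also fail to reconcile with the SAE reports made to the institution, the sponsor, the review board and the authorities under 14.4.2.

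**Working it through.** The protocol states no expected SAE rate, so there is no figure to reproduce. The check is a comparison of the texts, followed by a simple scale.

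**Step 1: compare the two definitions.**

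| Element | 8.1.7(4) and synopsis item (4) | 14.2 |
|---|---|---|
| Stem | Death or serious deterioration in health | Death or severe deterioration in health |
| Fatal illness or injury | Named | Named |
| Permanent damage to structure or function | Named | Named |
| Intervention to avoid permanent damage | Named (medical or surgical) | Named (medical) |
| Hospitalisation or prolonged stay | Not named | Named: "requirement for hospitalization or prolongation of hospitalization" |
| Fetal and congenital outcomes | Not named | Named |
| Exclusion of planned hospitalisation | None | Stated |

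The stems match, and the first three criteria are in substance the same. Hospitalisation is the difference that matters. Fetal and congenital outcomes should add little, because pregnant patients are excluded at entry (exclusion criterion 12).

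**Step 2: is this one endpoint or two?** Sections 4.2, 8.1.2 and 9.4.2 each list one endpoint of this kind and call it serious adverse events. The synopsis and 8.1.7 also list one and title it severe. It is therefore a single endpoint with two candidate definitions. No sentence in the protocol chooses between them.

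**Step 3: which subjects are affected?** Only subjects who meet all of these conditions:
- they have an unplanned admission or prolonged stay that is an SAE under 14.2;
- that event meets none of the three criteria listed in 8.1.7(4);
- they have no other event that qualifies under 8.1.7(4).

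**Step 4: scale.** Let k be the number of such subjects and N the size of the Safety Set.

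Difference in incidence (14.2 minus 8.1.7(4)) = 100 × k / N percentage points.

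With N = 90, the planned enrolment in 8.1.4.8 and 9.1.1:
- k = 1: 100 × 1/90 = 1.1 points
- k = 5: 100 × 5/90 = 5.6 points
- k = 10: 100 × 10/90 = 11.1 points

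The values 5 and 10 are arithmetic illustrations, not estimates. The protocol gives nothing from which k could be derived. If the Safety Set is smaller than 90, each subject weighs slightly more.

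**Step 5: when does the difference arise?** If the endpoint is programmed from the list in 8.1.7(4), the difference is 100 × k / N. If it is counted from the SAEs recorded under 14.2, the difference is zero.

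**The case against.** The case for leaving the text alone has four parts.

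**The list is not closed.** In 8.1.7(4) the test is death or serious deterioration, and the criteria follow the word including. Section 14.2 is built the same way. A reader might infer that an event serious only through hospitalisation is definitely excluded from the endpoint, but the text does not say so. This part stands: the defect is an ambiguity that permits exclusion. It does not remove the problem, because 14.2 uses the same construction and still names hospitalisation. Its absence from the otherwise parallel list invites different counts.

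**The usage elsewhere points to 14.2.** Three sections call the endpoint serious adverse events, the abbreviation list expands SAE in that way, and 14.2 is the only place that defines that exact term. No step is described that would remove hospitalisation-only SAEs before tabulation. This makes the 14.2 count plausible in practice, and it is why the under-count is conditional. It does not settle the matter, because 8.1.7(4) carries its own explicit definition and the conflict is never resolved.

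**The word severe does little harm.** A reader might infer a third count based on the 14.1.1 intensity grade. The documents do not support that: the title in 8.1.7(4) is followed at once by a definition about death or deterioration, and the headings of 14.2 and 14.4.2 use severe for the same concept. It is loose wording throughout the document, and at most two readings exist.

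**Many events would be captured anyway.** An endoleak or infection treated to prevent permanent harm can meet the intervention criterion. Type I and III endoleak is a separate endpoint (8.1.6(3)), ischaemic stroke within 30 days counts as a major adverse event (8.1.7(2)), and 9.4.2 requires all adverse events to be described and listed. This stands as a limit on the consequences: the events would still be visible in the report. The SAE percentage itself could still be too low.

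**Conclusion.** The inconsistency is real and should be corrected. The endpoint definition in 8.1.7(4) and the synopsis omits a criterion that 14.2 names, and the protocol does not say which applies.

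The consequence is conditional. If 8.1.7(4) is applied as a list, the SAE incidence is too low by about 1.1 percentage points for each subject whose only qualifying event is an unplanned admission or prolonged stay. This assumes a Safety Set of 90. If the count comes from the SAEs recorded under 14.2, there is no under-count. The total cannot be derived from the documents, and a reader who infers a shortfall of tens of points would be supplying the number of affected subjects from outside the protocol.

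The endpoint is descriptive, with no hypothesis test or performance criterion attached. The primary endpoint, the sample size and the success rule are unaffected.

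**What to change.** Replace the definition in 8.1.7(4) and in synopsis safety item (4) with: *incidence of serious adverse events as defined in section 14.2*. The endpoint and the safety reports then rest on one definition, including its exclusion of planned hospitalisation.

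As an accompanying wording correction, use *serious* for this concept throughout, including the headings of 14.2 and 14.4.2, and keep *severe* for the intensity grade in 14.1.1.

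The cost is a protocol wording change with the usual ethics committee approval. No new data are needed, because these events are already reportable under 14.2. The downside for the sponsor is a possibly less favourable SAE rate than a literal reading of 8.1.7(4) would give.
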